For **Cohort A**, we will use a randomized controlled trial for the use of a web based decision aid to give patients with sickle cell disease and parent/legal guardian of children with sickle cell disease accurate information about risks and benefits of therapies and enable them to make decisions based on their individual values and preferences. Participants will complete surveys before, soon after and within 4 months following their discussion with their health care provider to determine impact of the decision aid on knowledge, involvement in the decision and on decisional conflict, quality and uptake and adherence with the therapies.

For **Cohort B** we will use a mixed methods descriptive study design to determine the impact of the decision aid on quality and comprehension of information, and impact on daily life relating to management of sickle cell disease in patients <18 years of age.

Cohort C - To better understand the effect of the decision aid in decision making and patient involvement as reported by the physicians consenting these patients (child and adult) for treatment will be asked to participate in the study. Health care providers will not be randomized.

Randomization

After the consenting process is completed, adult participants will be assigned to **Cohort A** and will be randomized to the clinical trial control or intervention group. Further subdivision will be done by age, to include three age groups:

1. Parent/legal guardian of children (age group of child < 18 years)
2. Individuals with sickle cell disease =>18 years to <28 years
3. Individuals with sickle cell disease =>28 years

Participants <18 years will be assigned to **Cohort B** and will not be randomized.

Health care providers will be assigned to **Cohort C** and will not be randomized.

Cohort A

Consenting/Visit 1

After consenting in-person or via telephone, we will collect demographic information from adults with sickle cell disease including but not limited to age, gender, race, education, marital status, employment, religion, number of full and half siblings, as well as relationship, age and education of individual(s) who assists with sickle cell related healthcare decision making.

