Participants in Cohort A who are assigned to the control group will receive education regarding treatment consideration from their healthcare provider/team as per standard practice (usual care).

Participants in Cohort A who are assigned to the intervention group will receive education regarding treatment consideration from their healthcare provider/team as per standard practice. Additionally, they will be provided access to the decisional aid and will be provided with a unique access ID and password for purposes of this study. Participants will receive follow-up monthly via telephone call and/or e-mail to verify ability to access and navigate through website.

Visit 2

Participants will be scheduled for the second research visit to coincide with the completion of education presented by the healthcare provider/team. Participants will be asked to complete the study surveys within 2 weeks following the office/clinic visit via paper version or on-line. Self-report information regarding themselves or the patient they care for will be updated relating to sickle cell disease management and complications since Consent/Visit 1. Participants will receive follow-up monthly via telephone call and/or e-mail to verify ability to access and navigate through website.

Visit 3

Participants will be scheduled for the final research visit within 4 months of the completion of education and discussion with their healthcare provider/team. Participants will be asked to complete the study surveys as well as either via paper versions or online within 2 weeks following this office/clinic visit:

- Decision Regret Scale (*5 multiple choice*)
- Additionally, a qualitative interview will be conducted with the participants within 4 weeks of visit 3 to evaluate the extent to which the method of educational tools (standard practice or decision aid) helped the participant to recognize that a decision needs to be made regarding treatment of sickle cell disease, to understand the values that affect the decision, and understand if and how these values were addressed with the health care provider. Interviews will take approximately 30-45 minutes for completion. Interviews will

be audio recorded and transcribed verbatim for later analysis. Interviews will be conducted in a private setting, away from family members and clinical staff.

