After consenting in-person or via telephone, we will collect demographic information from children (<18 years of age) including but not limited to age, gender, race, education, number of full and half siblings as well as information about the parent/legal guardian of the child including but not limited to age, gender, race, education, marital status, employment, and religion.

Participants will be asked to complete the following study surveys within 2 weeks following each clinic/office visit:

- Decision Self-Efficacy Scale (*11 multiple choice*)
- Pediatric fatigue – short form 10a
- Pediatric mobility – short form 8a
- Pediatric pain interference – short form 8a
- Pediatric peer relationship – short form 8a
- Pediatric anxiety – short form 8b
- Pediatric depressive symptoms – short for 8b

Surveys may be available on-line for distant participation.

Visit 2

Participants will be scheduled for the second research visit to coincide with their next clinic appointment or within 4 months of Visit 1. Participants will be asked to complete the study surveys via paper version or online within 2 weeks following the office/clinic visit.

Self-report information regarding themselves or the patient they care for will be updated relating to sickle cell disease management and complications since Consent/Visit 1.

Visit 3

Participants will be scheduled for the final research within 4 months of Visit 2. Participants will be asked to complete the study surveys via paper version or online within 2 weeks following clinic/office visit.

Additionally, a qualitative interview will be conducted with the child within 4 weeks following visit 3 to understand the implications of education regarding sickle cell disease using the web-based decision aid tool on their daily lives: implementation of learned information to manage sickle cell disease, discussion with parent/legal guardian and/or healthcare provider regarding information gleaned from the decision aid tool, including conversations about potential treatment options. Interviews will take approximately 30-45 minutes for completion. Interviews will be audio recorded and transcribed verbatim for later analysis. Interviews will be conducted in a private setting, away from parents and clinical staff.

Self-report information regarding themselves or the patient they care for will be updated relating to sickle cell disease management and complications since Visit 2.

Cohort C

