5. Spouse, significant other, or other family member involved in decision making for child <18 years if parent/legal guardian of child already enrolled into this study.

Total number of subjects to be studied (including those screened for eligibility) in Qualitative Needs Assessment Interviews and Beta Testing:

Up to 50. Sample size is dependent on data saturation during analysis and need for verification of findings.

Total number of subjects to be studied in Hindi Beta Testing

Up to 50 individuals will be consented for participation in the Hindi Beta Testing study. Sample size is dependent on data saturation during analysis and need for verification of findings.

Total number of subjects to be studied (including those screened for eligibility) in Testing of Decision Aid:

Cohort A: 120

Cohort B: 25

Cohort C: Up to 50 (depending on number of health care providers providing care to patient population in this study).

Sample Size Calculations for the Randomized Clinical Trial (Cohort A)

We assume that patient involvement is 30% with standard care and we can double this with the intervention. Based on 90% power and 0.05 significance level we will require 110 patients, 55 in each group for comparing 2 binomial proportions⁴⁴. To account for attrition we propose to recruit 120 patients, 60 in each group treatment group with 20 in each of 3 age groups.

Total Duration of Participation

Qualitative Needs Assessment Interviews: 6 weeks

Decision Aid Testing: Up to 12 months

Recruitment Methods

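### Cohort A Visits 2 and 3 are dated only from completion of provider education, with no calendar backstop, so the between-arm comparison may be limited to participants selected after randomisation

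*Combined protocol and SAP*

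**What the plan says.** **Order of events.** Under Randomization, allocation follows consent: "After the consenting process is completed, adult participants will be assigned to" Cohort A and randomised. Both arms then receive education from their provider as in usual practice. For the intervention arm, "Additionally, they will be provided access to the decisional aid and will be provided with a unique access ID and password".

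**Cohort A follow-up.** Under Visit 2, "Participants will be scheduled for the second research visit to coincide with the completion of education presented by the healthcare provider/team". Under Visit 3, participants come for the "final research visit within 4 months of the completion of education and discussion with their healthcare provider/team". The design summary (Study Design for Testing of Decision Aid) uses the same anchor: "Participants will complete surveys before, soon after and within 4 months following their discussion with their health care provider". Expected Outcomes also counts its 4-month survey from the provider discussion. No section dates either visit from consent or randomisation, sets a deadline for finishing education, or says what happens if it is not finished.

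**Cohort B follow-up.** The non-randomised children have a "second research visit to coincide with their next clinic appointment or within 4 months of Visit 1".

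**Withdrawal from Study.** A participant may be withdrawn for not taking part in usual-care education. An intervention participant may be withdrawn for not viewing the website before the next scheduled appointment. Missing that appointment without rescheduling within 4 weeks is a further ground. Data up to withdrawal are kept and none are collected afterwards.

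**Other relevant text.** Total Duration of Participation gives "Decision Aid Testing: Up to 12 months". Avoidance of bias promises a drop-out analysis without stating a method.

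**The concern.** Randomisation protects the comparison only if outcomes are sought from everyone randomised, on a schedule that does not depend on what happens after allocation. Here the right to a Visit 2 or Visit 3 assessment depends on a later event. If education is never completed, neither visit falls due. The people affected are probably among the less engaged, which bears directly on involvement, knowledge and decisional conflict.

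The withdrawal rules point the same way. They can remove a participant for not taking part in education, and one ground, not viewing the website, can apply to the intervention arm only. Even with no loss at all, the arms could be assessed at different times since randomisation if education takes longer in one of them.

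At stake is whether the trial estimates the effect in all 120 randomised participants or in those who finished education.

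**Working it through.** **1. The plan's own figure.** Sample Size Calculations assumes involvement of 30% against 60%, 90% power and 0.05 significance, and gives 55 per group (110), with 120 recruited. A two-sided comparison of two proportions without continuity correction gives 56 per group (112), and 55 per group has 89.6% power. The stated figure is reproduced. The attrition allowance is 10/120 = 8.3%, or 5 of 60 per arm.

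**2. Does anything else trigger an assessment when education is not completed?**
- The 12-month duration is an upper limit and schedules nothing.
- The monthly contacts check website access only.
- The drop-out analysis works on data already collected.
- The withdrawal rules end data collection.
- Visit 1 surveys are due regardless of education, but in the design summary they are the before measurement.

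So no post-baseline assessment is scheduled for these participants.

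**3. Illustration of bias with no true effect.** Involvement is used because it is the sample-size outcome. The true rate is set at 30% in both arms (the plan's control rate). Completion *c* and involvement among non-completers *q* are assumptions, since the documents give neither.

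Rate among completers = (0.30 − (1 − c)·q) / c

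| q | c = 0.95 | c = 0.80 | Difference |
|---|---|---|---|
| 0 | 0.30/0.95 = 31.6% | 0.30/0.80 = 37.5% | 5.9 points |
| 0.10 | 0.295/0.95 = 31.1% | 0.280/0.80 = 35.0% | 3.9 points |

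The arm with lower completion looks better, so the sign depends on which arm that is. Over a wider range of non-completion:
- 10% against 20%: 2.8 to 4.2 points.
- 10% against 30%: 6.3 to 9.5 points.
- 10% in both arms with the same *q*: both arms read 33.3% (q = 0) or 32.2% (q = 0.10), and the difference is zero.

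**4. Power.** Loss of 20% takes 12 of 60 per arm, against the allowance of 5. At 30% against 60%, power is 89.6% with 55 per arm, 85.1% with 48 (20% lost) and 80.0% with 42 (30% lost).

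**5. Fit with the stated duration.** After education ends, a control participant's longest path is 4 months to Visit 3, 4 weeks to its interview, 4 weeks of Cross-Over and 4 weeks to that interview. The three 4-week periods total 84 days, or 2.76 months. Then 12 − 4 − 2.76 = 5.24 months is the latest that education could end if all of this must fit within 12 months. With Visit 2 no later than 4 months after Visit 1, the path is 4 + 4 + 2.76 = 10.76 months, or about 11.2 with the two-week Visit 2 survey window added.

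**The case against.** **Anchoring on education is a defensible choice.** The surveys are meant to follow the provider discussion closely, and Avoidance of bias relies on this to limit recall error. Acceptability of education and Preparation for Decision Making are hard to interpret before education ends. This stands, and is why the anchor should be kept and a backstop added.

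**The plan does address some non-completers.** Discretionary withdrawal covers several of these situations and a drop-out analysis is promised. This stands as a description, but withdrawal with no further data produces the same selection. It also means that a change to the visit schedule alone would not be enough.

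**The mechanism is not documented.** A reader might infer that the aid replaces provider education, or that providers know the allocation. The documents support neither. Both arms are to receive standard education, with the aid as an addition, and providers are said to learn of participation, not of arm. An effect of the aid on who completes, or when, is a reasonable inference and no more.

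**The size is assumed.** No completion rates are given, the direction is undetermined, and 4 to 6 points is small beside the planned 30. The involvement scale named under Expected Outcomes is also absent from the Cohort A survey list, so the illustration uses the sample-size outcome rather than a listed instrument. All of this stands.

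**Cohort B is only a partial precedent.** It is descriptive, and its rule does not say which of its two timings governs. It shows that a calendar alternative is workable in this study, not that a ready-made rule exists.

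**Conclusion.** The gap is real: both post-baseline assessments of the randomised cohort depend on a post-randomisation event and have no backstop. The withdrawal rules can deepen the resulting selection. The comparison may therefore be restricted to participants who completed education. Whether it is biased depends on losses, or outcomes among those lost, differing by arm, which the documents cannot settle. Under the assumptions shown, the bias is about 4 to 6 points (2.8 to 9.5 over the wider range), in either direction, and zero when losses and involvement among those lost are equal.

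Three stronger readings do not follow:
- **No outcome data at all.** Visit 1 surveys remain due; what is missing is a scheduled post-baseline assessment.
- **A faulty sample size.** The stated figure is reproduced, and power is still 85.1% with 20% lost in each arm.
- **A broken 12-month duration.** A conflict arises only if education ends more than about 5.2 months after consent and Cross-Over counts within the 12 months. The documents state neither.

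The sponsor should make the change. It matters for validity, but the size of the harm is unknown.

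**What to change.** - **Visit 2.** Keep it at completion of education. If education is not complete by 4 months after Visit 1, give the Visit 2 surveys then, on paper or online, to everyone randomised.
- **Visit 3.** Time it from the actual Visit 2 date. Nothing changes for participants whose Visit 2 coincides with completion.
- **Record and analyse.** Record at each survey whether education was complete. Compare all randomised participants in the main analysis, and add a sensitivity analysis by education status, read with caution because that status arises after randomisation.
- **Withdrawal.** Reconcile Withdrawal from Study with this schedule, so that not completing education or not viewing the website does not by itself end survey collection. Participants who withdraw consent are excepted.

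The cost is short edits to the visit schedule, the withdrawal section and the analysis section. No extra clinic attendance is needed and the education itself is unchanged. The main downside is that some Visit 2 surveys, including the education-specific scales, will be taken before education is finished. How many cannot be estimated, because the documents give no education durations.

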Self-report information regarding themselves or the patient they care for will be updated relating to sickle cell disease management and complications since Visit 2.

Cross-Over

After completion of final study visits/surveys and data collection, participants in the control group for Cohort A will be offered opportunity to visit the Decision Aid website. Participants will be given 4 weeks to review this site, at which time they will be asked to complete a series of questionnaires via paper version or electronically:

- Acceptability of education (*8 multiple choice, 2 short answer*)
- Decision Self-Efficacy Scale (*11 multiple choice*)
- Decisional Conflict Scale (*16 multiple choice*)
- Stage of Decision Making (*10 multiple choice*)
- Values survey (*14 multiple choice, 6 fill in the blank*)
- Realistic Expectations (*multiple choice*)
- Preparation for Decision Making Scale (*10 multiple choice*)
- Knowledge Survey (*25 multiple choice*)
- Choice Predisposition and Decision (*1 multiple choice and 4 fill in the blank*)
- Decision Regret Scale (*5 multiple choice*)

Participants => 18 years of age will complete:

- Emotional distress Anxiety – short form 6a – participant version
- Depression – short form 6a – participant version
- Fatigue – short form 6a – participant version
- Pain interference – short form 6a – participant version
- Physical Function – short form 8b – participant version
- Ability to participate in social roles and activities – short form 6a – participant version

Participants of children <18 years of age will complete:

- Fatigue – short form 10 – parent proxy
- Mobility – short form 8 – parent proxy
- Peer relations – short form 7 – parent proxy
- Anxiety – short form 8b – parent proxy
- Depressive symptoms – short form 6b – parent proxy

A qualitative interview will be conducted within 4 weeks of completion of the questionnaires to understand participant-perceived comparison of supportive care in decision making versus use of the Decision Aid tool. Participants will be asked to discuss the affect, if any, on their treatment decision prior to use of the Decision Aid tool. Participants will receive follow-up monthly via telephone call and/or e-mail to verify ability to access and navigate through website after receiving access to the decision aid.

Cohort B

Consenting/Visit 1

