After consenting to participate in the study in-person or via telephone demographic information will be collected from health care providers including but not limited to education, years of practice, age, and gender after Cohort A visit 3. Health care providers will be asked to complete one questionnaire after Cohort A visit 3 interview and again after Cohort A visit 4 interview. It is anticipated that this survey will take no more than 5 minutes to complete.

- Physician determination of patient readiness for treatment decision making in sickle cell disease

Study Population

Study population may be drawn from among sickle cell patients, any patient who is post-bone marrow transplant for sickle cell disease, and the caregivers of pediatric patients who receive care at the Aflac Cancer and Blood Disorders Center of Children's Healthcare of Atlanta (Egleston, Hughes Spalding, and Scottish Rite locations) and various sickle cell clinics across the United States. Contact will be made with physicians and sickle cell foundations through listserves, professional conferences, and seminars regarding this study. Recruitment flyers will be provided for placement in patient/parent/caregiver common areas to physicians, clinics, and sickle cell foundations known to the research team across the country after permission has been obtained from these entities. Recruitment flyers will request individuals to contact the research team if interested in participation. Discussion with physicians will occur prior to placement of flyers for Decision Aid website testing to obtain physician understanding of the study.

Recruitment of Women and Minorities as Research Subjects. Equal number of women and men are likely to be recruited. Majority of the patients will be of minority ethnic origin because of the demographics of distribution of SCD. The racial, gender and ethnic characteristics of the proposed subject population reflects the demographics of the study sites. We shall attempt to recruit subjects in respective proportion to these demographics. No exclusion shall be based on race, ethnicity, or gender.

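### Does the undefined Cohort A visit 4 leave the second provider questionnaire without a usable time point?

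*Combined protocol and SAP*

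**What the plan says.** Cohort C consists of health care providers, who are not randomized. Under Study Design for Testing of Decision Aid, its purpose is to learn about the "effect of the decision aid in decision making and patient involvement as reported by the physicians". Its only instrument is a short form on the patient's readiness to decide about treatment. The timing is given in the later Cohort C section: "Health care providers will be asked to complete one questionnaire after Cohort A visit 3 interview and again after Cohort A visit 4 interview".

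The Cohort A schedule reads differently:

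- **Visits.** There is Consenting/Visit 1, Visit 2 and Visit 3. Of Visit 3 the plan says "Participants will be scheduled for the final research visit within 4 months of the completion of education and discussion".
- **First interview.** Under Visit 3, "a qualitative interview will be conducted with the participants within 4 weeks of visit 3". This applies to both arms.
- **Cross-Over.** This step has no visit number. "After completion of final study visits/surveys and data collection, participants in the control group for Cohort A will be offered opportunity" to use the website. It closes with a second interview: "A qualitative interview will be conducted within 4 weeks of completion of the questionnaires".

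No section defines a visit 4 for any cohort.

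**The concern.** A data-collection point tied to a visit that does not exist has, read literally, no trigger, so no second form would ever fall due. If the intended trigger is the Cross-Over interview, a second issue appears. Only controls enter Cross-Over, so the second rating would have no counterpart in the intervention arm, and the Cohort C section does not say so.

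The stake would be the provider's view of the aid's effect. A reader might take the second rating for a two-arm comparison when it can only describe change within controls. Sites might omit the form, or look for it in the wrong arm.

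**Working it through.** The plan gives no figure for the number of provider forms, so there is none to reproduce. The check sets the schedule beside the Cohort C timing and then counts coverage.

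**Inputs**

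- Arm size: 60 per arm, from 3 age groups × 20 (Sample Size Calculations). Total 2 × 60 = 120.
- Before the attrition allowance: "we will require 110 patients, 55 in each group", so 2 × 55 = 110.
- Providers: at most 50 (total number of subjects, Cohort C).
- Assumption: one form per participant at each time point. The plan does not say whether forms are completed per participant or per provider. The form's subject, a patient's readiness, favours the former.

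**Step 1: what could visit 4 be?** The form is tied to an interview. Cohort A has exactly two: the one linked to Visit 3 and the one at the end of Cross-Over. The first is already used for the first rating, which leaves Cross-Over. The alternative is that the Cohort C section carries different numbering, so that its visits 3 and 4 are the present Visits 2 and 3. This fits less well, because consent is already Visit 1 and the present Visit 2 has no interview. The documents do not exclude it.

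**Step 2: coverage on each reading (upper limits)**

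| Reading | First rating | Second rating |
|---|---|---|
| Literal (no visit 4) | 60 + 60 = 120, after Visit 3 | 0 + 0 = 0 |
| Cross-Over interview | 60 + 60 = 120, after Visit 3 | 0 intervention + 60 control = 60, i.e. 60/120 = 50% |
| Shifted numbering | 60 + 60 = 120, at present Visit 2 | 60 + 60 = 120, after present Visit 3 |

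If the whole attrition allowance is used, the Cross-Over row becomes 110 first ratings and 0 + 55 = 55 second ratings, i.e. 55/110 = 50%. If each provider completes a single form, there are at most 50 at each time point. A provider caring for participants in both arms would then give a form that belongs to neither arm.

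**Step 3: what is common to all readings?** Each row contains a rating in both arms after the present Visit 3. That is the rating that allows the arms to be described side by side.

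**Step 4: does any planned result depend on the second rating?** Analytic Methods specifies no Cohort C analysis. The sample size rests on patient involvement in Cohort A alone. Nothing planned takes the second provider rating as an input.

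**The case for a change.** The strongest case for acting is that the error is certain and cheap to correct. The provider form is the only Cohort C instrument, one of its two administrations points to a visit that does not exist, and one sentence would name the step and the arms. The shifted-numbering reading does not rescue the text either, because the first form would then lack the interview it refers to.

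The fact stands: the reference is wrong on any reading. What does not follow is that the design is at fault. On the likeliest reading, controls receive the aid only after their final data collection, and rating them again after that new exposure is sensible. Intervention participants have no matching new exposure, so a second rating in their arm is not obviously missing. Correcting the label would leave the forms, participants and analyses as they are.

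Adding a second rating in both arms, for example at Visit 2, would be a different matter. It would mean up to 120 further forms at no more than 5 minutes each (120 × 5 = 600 minutes, or 10 hours in total) and earlier provider consent. It could also prompt providers before Visit 3. That is a trade-off the sponsor may weigh; it does not repair an error.

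The worry that sites would skip the form is conjecture. A coordinator who looks for the next interview after Visit 3 finds only one.

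**Conclusion.** This is a clerical slip, and no change to the plan follows. The visit 4 label is undefined, and the Cross-Over interview is its most likely meaning. On that reading the second rating covers at most 60 of 120 participants (55 of 110 with full attrition), all controls, and should be read as a within-control before-after description. These counts assume one form per participant, and they are ceilings because the website is only offered and providers must consent.

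The conclusion does not depend on which reading is right. A both-arm rating after the present Visit 3 is available on each of them, Cohort C has no specified analysis, and Cohort A's sample size and randomized outcomes are untouched. Whoever reports Cohort C should state when each rating was taken and in which arm, which an analyst would do in any case.
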